**4. Hospitalization**

If the subject was hospitalized, enter admission and discharge dates. Hospitalization is any in-patient hospital admission for medical reasons, including an overnight stay in a healthcare facility, regardless of duration. A pre-existing condition that did not worsen while on study, which involved a hospitalization for an elective treatment, is not considered an adverse event. Protocol specified hospitalizations are exempt. However, if the subject is retained in the study unit and becomes an inpatient due to an adverse event, the event would be reportable as a serious adverse event.

**5. Investigational Product including Lot # and Serial # when known / available**

Investigational Product – If applicable, indicate whether the Investigational Product is blinded or open-label

Initial Start Date – Enter date the product was first administered, regardless of dose.

Date of Dose Prior to or at the time of the Event – Enter date the product was last administered prior to, or at the time of, the onset of the event.

Action Taken with Product – Enter the status of the product administration.

Dose, Route, and Frequency at or prior to the event – Enter the appropriate information for the dose, route and frequency at, or prior to, the onset of the event.

**6. Concomitant Medications**

Indicate if there are any concomitant medications, including protocol-specified diluents and challenge agents.

Medication Name, Start Date, Stop Date, Dose, Route, and Frequency – Enter information for any other medications the subject is taking. Include any study drugs not included in section 5 (Product Administration) such as chemotherapy, which may be considered co-suspect.

Co-suspect – Indicate if the medication is suspect for the event

Continuing – Indicate if the subject is still taking the medication

Event Treatment – Indicate if the medication was used to treat the event

**7. Relevant Medical History**

Enter medical history that is relevant to the reported event, not the event description. This may include pre-existing conditions that contributed to the event allergies and any relevant prior therapy, such as radiation. Include dates if available.

**8. Relevant Laboratory Tests**

Indicate if there are any relevant laboratory values.

For each test type, enter the test name, units, date the test was run and the results.

**9. Other Relevant Tests**

Indicate if there are any tests, including any diagnostics or procedures.

For each test type, enter the date, name, results and units (if applicable).

**10. Case Description**

Describe Event – Enter summary of the event. Provide narrative details of the events listed in section 3. Include any therapy administered, such as radiotherapy; (excluding medications, which will be captured in section 6). If necessary, provide additional pages to Amgen.

**Footer**

Signature, Title and Date\* – The Investigator or designee must sign the form and provide his or her title and date and fax form to Amgen. If the reporter is not the Investigator, Designee must be identified on the Delegation of Authority form.

A 20210249 (TNB585.001) AMG 340/TNB-585	Clinical Trial Serious Adverse Event Report – Phase 1–4 Notify Amgen Within 24 Hours of knowledge of the event			 New  Follow-up
--	---	--	--	--

<<Fax number to be populated by COM/Study Manager/Protocol Author prior to providing to sites>> SELECT OR TYPE IN A FAX#										
1. SITE INFORMATION										
Site Number	Investigator				Country		Date of Report Day      Month      Year			
Reporter			Phone Number (      )			Fax Number (      )				
2. SUBJECT INFORMATION										
Subject ID Number	Age at event onset				Sex  F  M	Race		If applicable, provide End of Study date		
3. SERIOUS ADVERSE EVENT - Information in this section must also be entered on the Serious Adverse Event Summary CRF										
Provide the date the Investigator became aware of this Serious Adverse Event Information: Day      Month      Year										
Serious Adverse Event Diagnosis or Syndrome  If diagnosis is unknown, enter Signs / Symptoms  When Final Diagnosis is known, enter as Adverse Event  List one event per line. If event is fatal, enter the Cause of Death. Entry of "Death" is not acceptable, as this is an outcome.	Date Started	Date Ended	Check only if event not comed before first date of IP	Enter Status Other code (see codes below)	Relationship Is there a reasonable possibility that the event may have been caused by IP or an Amgen device used to administer the IP?				Outcome of Event  01 Resolved 02 Not resolved 03 Fatal 04 Unknown	Check only if event is related to study procedure, e.g. biopsy
					AMG 340	68Ga-PSMA-11	18F-FDG	<IP/Device>		
Day      Month      Year	Day      Month      Year									
Serious Criteria: 01 Fatal 02 Immediately life- threatening 03 Required hospitalization 04 Prolonged hospitalization		03 Persistent or significant disability /incapacity 06 Congenital anomaly / birth defect		05 Other medically important serious event						
4. HOSPITALIZATION										
Was subject hospitalized or was a hospitalization prolonged due to this event?  No  Yes, If yes, please complete date(s):					Date Admitted Day      Month      Year	Date Discharged Day      Month      Year				
5. INVESTIGATIONAL PRODUCT (IP)										
AMG 340/TNB-585 \Open Label	Initial Start Date  Day      Month      Year	Prior to, or at time of Event				Action Taken with Product  01 Still being Administered 02 Permanently discontinued 03 Withheld	Lot # and Serial #			
		Date of Dose Day      Month      Year	Dose	Route	Frequency					
68Ga-PSMA-11 \Open Label							Lot # _____  Unknown Serial # _____  Unknown			
18F-FDG \Open Label							Lot # _____  Unknown Serial # _____  Unknown			
<<IP/Device>>  Blinded  Open Label										

A 20210249 (TNB585.001) AMG 340/TNB-585	Clinical Trial Serious Adverse Event Report – Phase 1–4 Notify Amgen Within 24 Hours of knowledge of the event										 New  Follow-up	
		Site Number			Subject ID Number							
6. CONCOMITANT MEDICATIONS (eg, chemotherapy) Any Concomitant Medications?  No  Yes, If yes, please complete:												
Medication Name(s)		Start Date Day Month Year	Stop Date Day Month Year	Co-suspect  Now  Yes	Continuing  Now  Yes	Dose	Route	Freq	Treatment Med  Now  Yes			
7. RELEVANT MEDICAL HISTORY (include dates, allergies and any relevant prior therapy)												
8. RELEVANT LABORATORY VALUES (include baseline values) Any Relevant Laboratory values?  No  Yes, If yes, please complete:												
Date Day Month Year	Test											
	Unit											
9. OTHER RELEVANT TESTS (diagnostics and procedures) Any Other Relevant tests?  No  Yes, If yes, please complete:												
Date Day Month Year	Additional Tests				Results				Units			

A 20210249 (TNB585.001) AMG 340/TNB-585	Clinical Trial Serious Adverse Event Report – Phase 1–4 Notify Amgen Within 24 Hours of knowledge of the event				 New  Follow-up
	Site Number		Subject ID Number		
10. CASE DESCRIPTION (Provide narrative details of events listed in section 3) For each event in section 3, where relationship=Yes, please provide rationale.					
Signature of Investigator or Designee					
I confirm by signing this report that the information on this form, including seriousness and causality assessments, is being provided to Amgen by the investigator for this study, or by a Qualified Medical Person authorized by the investigator for this study.					
Title					
Date					

## **11.5 Appendix 5. Contraceptive Guidance and Collection of Pregnancy and Lactation Information**

Study-specific contraception requirements for males are outlined in Section [5.2](#).

Contraceptive use and methods should be consistent with local regulations for subjects participating in clinical studies.

Male subjects should be advised of the pregnancy prevention requirements and the potential risk to the fetus if they father a child during treatment and for 6 months after the last dose of protocol-required therapies.

### **Definition of Females of Childbearing Potential**

A female is considered fertile following menarche and until becoming postmenopausal unless permanently sterile. Permanent sterilization methods include documented hysterectomy, bilateral salpingectomy, and bilateral oophorectomy. Females with documented permanent infertility due to an alternate medical cause (eg, Mullerian agenesis, androgen insensitivity, gonadal dysgenesis), can be considered not of childbearing potential.

**Note:** Bilateral tubal ligation/occlusion is not considered a permanent sterilization method.

**Note:** Documentation from the following sources is acceptable to provide confirmation of each sterilization method: 1) review of subject's medical records; 2) subject's medical examination; or 3) subject's medical history interview.

A postmenopausal female is defined as:

- A woman of  $\geq 55$  years with no menses for 12 months without an alternative medical cause OR
- A woman age  $< 55$  years with no menses for at least 12 months and with a follicle-stimulating hormone (FSH) level within the definition of "postmenopausal range" for the laboratory involved. In the absence of 12 months of amenorrhea, confirmation with more than 1 FSH measurement is required.

## Contraception Methods for Females

### Highly Effective Contraceptive Methods

- Combined (estrogen and progestogen containing) hormonal contraception associated with inhibition of ovulation (oral, intravaginal, or transdermal)
- Progestogen-only hormonal contraception associated with inhibition of ovulation (oral, injectable, or implantable)
- Intrauterine device
- Intrauterine hormonal-releasing system
- Bilateral tubal ligation/occlusion
- Vasectomized partner (provided that partner is the sole sexual partner of the female subject of childbearing potential and that the vasectomized partner has received medical assessment of the surgical success)
- Sexual abstinence (defined as refraining from heterosexual intercourse during the entire period of risk associated with the study treatments; the reliability of sexual abstinence must be evaluated in relation to the duration of the trial and the preferred and usual lifestyle of the subject)

### Contraception Methods for Male Subjects

- Sexual abstinence (defined as refraining from heterosexual intercourse during the entire period of risk associated with protocol-required therapies; the reliability of sexual abstinence must be evaluated in relation to the duration of the trial and the preferred and usual lifestyle of the subject)
- Use a condom during treatment and for an additional 6 months after the last dose of protocol-required therapies

The female partner should consider using a method of contraception for female subjects stated above (a female condom should not be used because there is a risk of tearing when both partners use a condom).

Note: If the male's sole female partner is of non-childbearing potential or has had a bilateral tubal ligation/occlusion, he is not required to use additional forms of contraception during the study.

## Collection of Pregnancy Information

### Male Subjects With Partners Who Become Pregnant or Were Pregnant at the Time of Enrollment

- In the event a male subject fathers a child during treatment, and for an additional 6 months after discontinuing protocol-required therapies, the information will be recorded on the Pregnancy Notification Form. The form (see [Figure 11-2](#)) must be submitted to Amgen Global Patient Safety immediately and no later than 24 hours of the site's awareness of the pregnancy. (Note: Sites are not required to provide any information on the Pregnancy Notification Form that violates the country or regions local privacy laws).

- Males with pregnant partners or whose partners become pregnant during treatment and for an additional 6 months after the last dose of protocol-required therapies must practice sexual abstinence or use a condom through 6 months after the last dose of protocol-required therapies.
- The investigator will attempt to obtain a signed consent for release of pregnancy and infant health information directly from the pregnant female partner to obtain additional pregnancy information.
- After obtaining the female partner's signed consent for release of pregnancy and infant health information, the investigator will collect pregnancy outcome and infant health information on the pregnant partner and her baby and complete the pregnancy questionnaires. This information will be forwarded to Amgen Global Patient Safety.
- Generally, infant follow-up will be conducted up to 12 months after the birth of the child (if applicable).
- Any termination of the pregnancy will be reported to Amgen Global Patient Safety regardless of fetal status (presence or absence of anomalies) or indication for procedure.

### Figure 11-2. Pregnancy Notification Form

Amgen Proprietary - Confidential

##### 1. Case Administrative Information

Protocol/Study Number: **20210249 (TNB585.001)**

Study Design:  Interventional  Observational (If Observational:  Prospective  Retrospective)

##### 3. Subject Information

Subject ID # \_\_\_\_\_ Subject Gender:  Female  Male Subject age (at onset): \_\_\_\_\_ (in years)

##### 4. Amgen Product Exposure

Amgen Product	Dose at time of conception	Frequency	Route	Start Date
AMG 340 / TNB-585				mm ____ /dd ____ /yyyy ____

Was the Amgen product (or study drug) discontinued?  Yes  No

If yes, provide product (or study drug) stop date: mm \_\_\_\_ /dd \_\_\_\_ /yyyy \_\_\_\_

Did the subject withdraw from the study?  Yes  No

##### 5. Pregnancy Information

Pregnant female's last menstrual period (LMP) mm \_\_\_\_ /dd \_\_\_\_ /yyyy \_\_\_\_  Unknown  N/A

Estimated date of delivery mm \_\_\_\_ /dd \_\_\_\_ /yyyy \_\_\_\_

If N/A, date of termination (actual or planned) mm \_\_\_\_ /dd \_\_\_\_ /yyyy \_\_\_\_

Has the pregnant female already delivered?  Yes  No  Unknown  N/A

If yes, provide date of delivery: mm \_\_\_\_ /dd \_\_\_\_ /yyyy \_\_\_\_

Was the infant healthy?  Yes  No  Unknown  N/A

If any Adverse Event was experienced by the infant, provide brief details:

##### Form Completed by:

Print Name: \_\_\_\_\_ Title: \_\_\_\_\_

Signature: \_\_\_\_\_ Date: \_\_\_\_\_

## **11.6 Appendix 6. Sample Storage and Destruction**

Any blood (eg, biomarker, pharmacokinetics) sample collected according to the Schedule of Activities (Section 1.3) can be analyzed for any of the tests outlined in the protocol and for any tests necessary to minimize risks to study subjects. This includes testing to ensure analytical methods produce reliable and valid data throughout the course of the study. This can also include, but is not limited to, investigation of unexpected results, incurred sample reanalysis, and analyses for method transfer and comparability.

All samples and associated results will be coded prior to being shipped from the site for analysis or storage. Samples will be tracked using a unique identifier that is assigned to the samples for the study. Results are stored in a secure database to ensure confidentiality.

If informed consent is provided by the subject, Amgen can do additional testing on remaining samples (ie, residual and back-up) to investigate and better understand the metastatic castrate-resistant prostate carcinoma, the dose response and/or prediction of response to AMG 340, and characterize aspects of the molecule (eg, mechanism of action/target, metabolites). Results from this analysis are to be documented and maintained, but are not necessarily reported as part of this study. Samples can be retained for up to 20 years.

Since the evaluations are not expected to benefit the subject directly or to alter the treatment course, the results of pharmacogenetic, biomarker development, or other exploratory studies are not placed in the subject's medical record and are not to be made available to the subject, members of the family, the personal physician, or other third parties, except as specified in the informed consent.

The subject retains the right to request that the sample material be destroyed by contacting the investigator. Following the request from the subject, the investigator is to provide the sponsor with the required study and subject number so that any remaining sample types (eg, blood, tumor) samples and any other components from the cells can be located and destroyed. Samples will be destroyed once all protocol-defined procedures are completed. However, information collected from samples prior to the request for destruction, will be retained by Amgen.

The sponsor is the exclusive owner of any data, discoveries, or derivative materials from the sample materials and is responsible for the destruction of the sample(s) at the

request of the subject through the investigator, at the end of the storage period, or as appropriate (eg, the scientific rationale for experimentation with a certain sample type no longer justifies keeping the sample). If a commercial product is developed from this research project, the sponsor owns the commercial product. The subject has no commercial rights to such product and has no commercial rights to the data, information, discoveries, or derivative materials gained or produced from the sample.

See Section [11.3](#) for subject confidentiality.

**11.7 Appendix 7. Hepatotoxicity Stopping Rules: Suggested Actions and Follow-up Assessments and Study Treatment Rechallenge Guidelines**

Subjects with abnormal hepatic laboratory values (ie, alkaline phosphatase [ALP], aspartate aminotransferase [AST], alanine aminotransferase [ALT], total bilirubin [TBL]) and/or international normalized ratio (INR) and/or signs/symptoms of hepatitis (as described below) may meet the criteria for withholding or permanent discontinuation of Amgen investigational product or other protocol-required therapies, as specified in the *Guidance for Industry Drug-Induced Liver Injury: Premarketing Clinical Evaluation, July 2009*.

**Criteria for Withholding and/or Permanent Discontinuation of Amgen Investigational Product and Other Protocol-required Therapies Due to Potential Hepatotoxicity**

The following stopping and/or withholding rules apply to subjects for whom another cause of their changes in liver biomarkers (TBL, INR and transaminases) has not been identified.

Important alternative causes for elevated AST/ALT and/or TBL values include, but are not limited to:

- Hepatobiliary tract disease
- Viral hepatitis (eg, hepatitis A/B/C/D/E, Epstein-Barr Virus, cytomegalovirus, herpes simplex virus, varicella, toxoplasmosis, and parvovirus)
- Right sided heart failure, hypotension or any cause of hypoxia to the liver causing ischemia
- Exposure to hepatotoxic agents/drugs or hepatotoxins, including herbal and dietary supplements, plants and mushrooms
- Heritable disorders causing impaired glucuronidation (eg, Gilbert's syndrome, Crigler-Najjar syndrome) and drugs that inhibit bilirubin glucuronidation (eg, indinavir, atazanavir)
- Alpha-1 antitrypsin deficiency
- Alcoholic hepatitis
- Autoimmune hepatitis
- Wilson's disease and hemochromatosis
- Nonalcoholic fatty liver disease including steatohepatitis
- Non-hepatic causes (eg, rhabdomyolysis, hemolysis)

If investigational product(s) is/are withheld, the subject is to be followed for possible drug induced liver injury (DILI) according to recommendations in the last section of this appendix.

Rechallenge may be considered if an alternative cause for impaired liver tests (ALT, AST, ALP) and/or elevated TBL, is discovered and the laboratory abnormalities resolve to normal or baseline (see next section in this appendix).

**Table 11-3. Conditions for Withholding and/or Permanent Discontinuation of Amgen Investigational Product and Other Protocol-required Therapies Due to Potential Hepatotoxicity**

Analyte	Temporary Withholding	Permanent Discontinuation
TBL	> 3x ULN at any time	> 2x ULN  OR
INR	--	> 1.5x (for subjects not on anticoagulation therapy)  AND
AST/ALT	> 8x ULN at any time  > 5x ULN but < 8x ULN for $\geq$ 2 weeks  > 5x ULN but < 8x ULN and unable to adhere to enhanced monitoring schedule  > 3x ULN with clinical signs or symptoms that are consistent with hepatitis (such as right upper quadrant pain/tenderness, fever, nausea, vomiting, and jaundice)	In the presence of no important alternative causes for elevated AST/ALT and/or TBL values  > 3x ULN (when baseline was < ULN)
ALP	> 8x ULN at any time	--

ALP = alkaline phosphatase; ALT = alanine aminotransferase; AST = aspartate aminotransferase; INR = international normalized ratio; TBL = total bilirubin; ULN = upper limit of normal

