## **5.1 Inclusion Criteria**

Subjects are eligible to be included in the study only if all of the following criteria apply:

- 101 Subject must be  $\geq$  18 years of age at the time of signing informed consent.
- 102 Subject has a history of pathologically confirmed prostatic adenocarcinoma.
- 103 Subject has history of metastatic disease.
- 104 Subject is chemically or surgically castrate (testosterone  $\leq$  0.5 ng/mL or 1.7 nmol/L). Subjects must continue on an LHRH/GnRH agonist or antagonist while on study unless they are surgically castrate.
- 105 Subject has received at least 2 lines of systemic therapy approved for mCRPC, with disease progression on the most recent systemic therapy as defined in PCWG3. Subjects should have previously been exposed to, intolerant of, ineligible for, or declined therapy with both a novel anti-androgen (eg, abiraterone, enzalutamide) and a taxane (eg, docetaxel).
- 106 Subject has an Eastern Cooperative Oncology Group (ECOG) Performance Status of  $\leq$  2 (see Section 11.8).
- 107 Subject has provided informed consent/assent prior to initiation of any study specific activities/procedures.
- 108 Subject must have adequate bone marrow function, defined as: absolute neutrophil count (ANC)  $\geq$  1500/mm^3; platelets  $\geq$  100 000/mm^3 (without platelet transfusion within 7 days from screening assessment); hemoglobin  $\geq$  9.0 g/dL (without blood transfusion within 7 days from screening assessment).
- 109 Subject must have an eGFR  $\geq$  50 mL/min as estimated by the MDRD formula. Note: Per FDA draft guidance, 'renal impairment is not likely to alter PK enough to justify dosage adjustment' for protein therapeutics  $>$  69 kDa, specifically including antibodies, such as AMG 340 (FDA 2020).
- 110 Subject must have total bilirubin  $\leq$  1.5  $\times$  upper limit of normal (ULN; except if the subject has a known diagnosis of Gilbert's syndrome, in which case bilirubin must be  $<$  3  $\times$  ULN). Aspartate aminotransferase (AST) and alanine aminotransferase (ALT) must be  $\leq$  3  $\times$  ULN (except if the subject has a known diagnosis of Gilbert's syndrome or liver metastases, in which case AST/ALT must be  $<$  5  $\times$  ULN).

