### **Criteria for Rechallenge of Amgen Investigational Product and Other Protocol-required Therapies After Potential Hepatotoxicity**

The decision to rechallenge the subject is to be discussed and agreed upon unanimously by the subject, investigator, and Amgen.

If signs or symptoms recur with rechallenge, then Amgen investigational product and other protocol-required therapies, as appropriate is to be permanently discontinued. Subjects who clearly meet the criteria for permanent discontinuation (as described in [Table 11-3](#)) are never to be rechallenged.

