## Drug-induced Liver Injury Reporting and Additional Assessments

### Reporting

To facilitate appropriate monitoring for signals of DILI, cases of concurrent AST or ALT and TBL and/or INR elevation, according to the criteria specified in the above, require the following:

- The event is to be reported to Amgen as a serious adverse event immediately and no later than 24 hours of discovery or notification of the event (ie, before additional etiologic investigations have been concluded)
- The appropriate case report form (CRF) (eg, Events CRF) that captures information necessary to facilitate the evaluation of treatment-emergent liver abnormalities is to be completed and sent to Amgen

Other events of hepatotoxicity and potential DILI are to be reported as serious adverse events if they meet the criteria for a serious adverse event defined in Section [11.4](#).

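### Table 11-3 sets no permanent-discontinuation threshold for subjects whose baseline AST/ALT was at or above ULN, although criterion 110 admits baselines up to 3x ULN

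*Protocol*

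**What the plan says.** All of the text is in the Protocol.

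- **Permanent discontinuation (Table 11-3).** TBL > 2x ULN, or INR > 1.5 in a subject not on anticoagulants, together with AST/ALT "> 3x ULN (when baseline was < ULN", and no important alternative cause. The Criteria for Rechallenge rule out any rechallenge after this.
- **Temporary withholding (Table 11-3), with no baseline condition.** TBL > 3x ULN; AST/ALT > 8x; AST/ALT above 5x and below 8x for 2 weeks or more, or if enhanced monitoring cannot be followed; AST/ALT > 3x "with clinical signs or symptoms that are consistent with hepatitis"; ALP > 8x. INR has no withholding entry.
- **Scope (Section 11.7).** "The following stopping and/or withholding rules apply to subjects for whom another cause of their changes in liver biomarkers" has not been identified. The open list of alternative causes includes "Heritable disorders causing impaired glucuronidation (eg, Gilbert's syndrome".
- **Eligibility (Section 5.1, criterion 110).** AST and ALT up to 3x ULN. The exception is a "known diagnosis of Gilbert's syndrome or liver metastases, in which case AST/ALT must be" below 5x ULN.
- **Restart after withholding (Section 11.7).** "Rechallenge may be considered if an alternative cause for impaired liver tests (ALT, AST, ALP) and/or elevated TBL, is discovered" and the values have returned to normal or baseline. The decision must be "agreed upon unanimously by the subject, investigator" and sponsor.
- **Close observation (Section 11.7).** Required for AST or ALT > 3x ULN, or for a 2-fold rise in subjects whose values were raised before drug. Liver tests are repeated every 24 hours if TBL > 2x ULN or INR > 1.5.
- **Table 6-6, hepatotoxicity row.** Gives no thresholds and refers back to Section 11.7.

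**The concern.** The permanent-stop rule targets unexplained transaminase elevation together with raised bilirubin or INR. Its baseline condition removes subjects whom the eligibility criteria deliberately admit, and nothing replaces it for them. Two subjects with the same on-treatment values, with drug cause not excluded in either, are therefore handled differently. One is stopped for good. The other may have no Table 11-3 action at all, although the starting liver tests were worse.

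The close-observation text names subjects with raised values before drug and gives them a baseline-relative rule. So the appendix foresaw this group for observation but gave it no entry in the permanent column.

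Reporting may be affected too. The automatic 24-hour serious-event report covers "cases of concurrent AST or ALT and TBL and/or INR elevation, according to the criteria specified in the above". If that phrase points to the Table 11-3 criteria, which is the natural reading, these subjects also miss the automatic report. The general serious-adverse-event definition would still apply.

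Liver effects are not remote here. Table 2-2 lists transaminitis and hyperbilirubinemia among the signs of CRS, the identified risk. Section 2.2.4.3 reports serious AST increase in 2 of 23 dosed subjects and serious ALT increase in 1.

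**Working it through.** No sample-size or error-rate figure is involved, so the check sets the rules side by side. Write b for baseline AST/ALT, A for on-treatment AST/ALT and T for TBL, all in multiples of ULN.

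**Rules, with no alternative cause and no anticoagulant**

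- Permanent = (T > 2 or INR > 1.5) and A > 3 and b < 1.
- Withhold = T > 3, or A > 8, or 5 < A < 8 for at least 2 weeks (or without enhanced monitoring), or A > 3 with hepatitis-type symptoms, or ALP > 8x ULN.

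Because b < 1 is a required part of the permanent rule, that rule is false for every b at or above 1, whatever A, T and INR are.

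**Cases: asymptomatic unless stated, enhanced monitoring followed, ALP normal**

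| A | T | INR | b = 0.9 | b = 1.2 |
|---|---|---|---|---|
| 4.5 | 2.5 | normal | permanent | no action at 7, 14 or 28 days |
| 4.5 | 1.0 | 1.6 | permanent | no action at 7, 14 or 28 days |
| 4.5, with symptoms | 2.5 | normal | permanent | withhold |
| 7 | 2.5 | normal | permanent | no action at 7 days, withhold at 14 |
| 9 | 2.5 | normal | permanent | withhold |
| 4.5 | 3.5 | normal | permanent | withhold |

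Baselines of 1.0x, 2.0x and 2.9x give the same results as 1.2x.

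**The band with no Table 11-3 action (b at or above 1)**

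- T above 2 and up to 3, or INR > 1.5 off anticoagulants with T up to 3; and
- A above 3 and up to 5 at any duration, or A above 5 and below 8 for under 2 weeks; and
- no hepatitis-type symptoms, enhanced monitoring followed, ALP no higher than 8x, no alternative cause.

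With b < 1, every value set in this band means permanent discontinuation.

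**Who is affected.** Gilbert's syndrome is a listed alternative cause, so those subjects may fall outside both columns at any baseline. Liver metastases are not listed, but the list is open, so the same may hold for them. The core group is therefore baseline 1x to 3x ULN without either diagnosis.

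**Close observation.** Going from 1.2x to 4.5x is a 4.5/1.2 = 3.75-fold rise and exceeds 3x ULN, so close observation applies on either limb. It brings testing and a search for causes; it does not itself stop dosing.

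**General rules that could act instead**

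| Place | What it does | Why it does not replace the missing entry |
|---|---|---|
| 6.2.1.4 | Holds drug for DLT-equivalent non-hematologic events; resumption one level lower with Medical Monitor approval; at most 2 reductions | Reach depends on CTCAE grades that the documents do not reproduce; 6.2.1.4.1.1 exempts ALT-type laboratory events that are not clinically relevant and improve to grade 2 or lower within 7 days |
| 6.2.1.4 and 7.1 | Discontinuation for a delay over 14 days | Needs dosing to have been held already |
| 6.2.1.6.1.2 | Lets the investigator treat as a DLT any drug-related toxicity thought to warrant withholding | Discretionary, no threshold |
| Table 6-6, other related events of grade 3 or higher | Interrupts if judged intolerable or clinically significant and unresponsive to management; may resume at the same dose; permanent stop after more than 2 consecutive missed doses, recurrence at grade 4, or a repeat grade 3 or higher event despite reduction | Not tied to bilirubin or INR |
| 11.7, Criteria for Rechallenge | Permanent stop if signs or symptoms recur on rechallenge | Needs an earlier hold |

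**The case against.** The strongest defense is that the baseline condition is explicit and looks deliberate, and that the protocol has other safeguards. Subjects with raised baselines get their own observation pathway, with daily retesting once TBL passes 2x ULN or INR passes 1.5. The general rules above contain real permanent stops with no baseline condition. Dosing is every 3 weeks outside cycle 1 priming, so an elevation in the 5x to 8x range that begins in the first week of a cycle and persists reaches the 2-week withholding trigger before the next dose. The cited 2009 liver-injury guidance is not available here, so no departure from it can be claimed.

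Much of this stands, and it limits how far the point can be pushed. A reader might infer that subjects with a raised baseline can never be permanently discontinued for liver toxicity, or have only the withholding triggers to protect them. The documents do not support that:

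- The table does not say whose baseline counts when only one of AST and ALT was raised. A subject with raised AST and normal ALT at entry could arguably qualify through ALT.
- Withholding alone is true of Table 11-3, not of the whole protocol.
- Subjects with Gilbert's syndrome, and possibly those with liver metastases, may be outside the rules for another reason, so the 5x limit should not be used to enlarge the group.

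Nor do the data show harm. Section 2.2.4.3 names no bilirubin or INR event among the common, severe or serious events it lists. Nausea in 13 and vomiting in 12 of 23 subjects suggest that the symptom trigger may often be available, but those counts are not tied to raised transaminases and cannot size the gap.

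The defense does not supply the missing entry. Observation is not a stop, and the 3-week interval does not help in the 3x to 5x range, where no duration triggers anything in the table.

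**Conclusion.** The point holds for Table 11-3 read literally. It has no permanent-discontinuation threshold for baseline AST/ALT at or above ULN, and for part of the value range no withholding trigger fills the space. The contrast is clearest when both AST and ALT were raised at entry, to between 1x and 3x ULN, without Gilbert's syndrome or liver metastases.

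The practical band is narrow, and the number of subjects in it cannot be derived from the documents. The conclusion assumes no identified alternative cause, no hepatitis-type symptoms, enhanced monitoring followed, ALP no higher than 8x ULN and, for the INR route, no anticoagulant. Investigators and the Medical Monitor may well stop such a subject under the general rules. The weakness is that the liver-specific rule does not require it, while requiring it for the same values in someone who entered with normal tests. That merits correction in the next amendment.

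**What to change.** Add an AST/ALT entry for baseline at or above ULN to the permanent-discontinuation column, for example AST/ALT > 3x ULN and at least 2x baseline. Keep the same TBL/INR and no-alternative-cause conditions. State that the baseline of the analyte that rises is the one that counts, and that the rechallenge ban and the 24-hour reporting rule apply to the new entry.

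The 2-fold multiple already appears in the close-observation text, but there it governs observation, not stopping. The sponsor's safety team should therefore set the final value. With multiple m, the trigger is the larger of 3 and m x b. The share of the 3x to 8x range it closes is (8 - trigger)/5, which is a width of values, not a share of subjects.

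| Baseline (x ULN) | Trigger, m = 2 | Closed | Trigger, m = 1.5 | Closed |
|---|---|---|---|---|
| 1.5 | 3 | 100% | 3 | 100% |
| 2.0 | 4 | 80% | 3 | 100% |
| 2.5 | 5 | 60% | 3.75 | 85% |
| 3.0 | 6 | 40% | 4.5 | 70% |

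The trade-off is visible at a baseline of 2.9x. A rise to 4.5x is 4.5/2.9 = 1.55-fold, which triggers at m = 1.5 but not at m = 2.

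The cost is one table entry and a short clarifying text in an amendment, with no new tests. The downside is that a few subjects with abnormal baselines may be stopped who would otherwise have continued.
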